#### **14.2.2.3.1 Relationship between Re[in]jection Intervals and Effectiveness**

Analysis will be performed considering each Ozurdex reinjection separately (second injection or first reinjection, third injection or second reinjection...) (see Figure 1).

Change in BCVA from time of reinjection to 7-12 weeks following reinjection and change in BCVA from time of first injection to 7-12 weeks following reinjection will be summarized for each reinjection. The same analyses will be performed for the change in CRT.

A first approach to assess the relationship between reinjections intervals and effectiveness will be to consider time interval between two injections (previous injection - reinjection) as a continuous parameter. The potential relationship between time interval and effectiveness will be assessed graphically using a scatter plot. Time interval between two injections (in months) will be plotted on the horizontal axis and either BCVA change or CRT change from time of reinjection to 7-12 weeks following reinjection will be plotted on the vertical axis. The corresponding correlation coefficients will be calculated. The same scatter plot will be done for the change in BCVA and CRT from time of first implant injection to 7-12 weeks following each Ozurdex implant injection.

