**Figure 1 Example of Reinjections Intervals and Effectiveness Outcomes Disposition in a Hypothetic Patient**

BCVA=Best corrected visual acuity; CRT=Central retinal thickness

- Last BCVA and CRT measured before injection of Ozurdex
- BCVA and CRT measured 7 to 12 weeks following each reinjection

For "Time interval 1", BCVA and CRT change from measurement 1 to measurement 2 will be considered; for "Time interval 2" BCVA and CRT change from measurement 3 to measurement 4 will be considered; and for "Time interval 3", BCVA and CRT change from measurement 5 to measurement 6 will be considered.

A second approach will be to consider time interval between two injections as a categorical variable; either 2 categories will be considered based on median time interval or other categories will be considered based on observed distribution. BCVA change and CRT change from reinjection to 7-12 weeks following reinjection and BCVA and CRT change from time of first implant injection to 7-12 weeks following each Ozurdex implant injection will be described by these categories.

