## 15.2 ANALYSIS OF THE SECONDARY OBJECTIVES

### 15.2.1 First Secondary Objective

The secondary objective '*To assess the relationship between reinjection intervals and drug effectiveness*' will be assessed considering the following outcomes:

- Re[injection interval in months defined for each reinjection in the study eye (see definition in Section 15.1)
- For effectiveness (in the study eye):
  - BCVA change (ETDRS letters) from the last assessment prior to Ozurdex injection to 7–12 weeks following each Ozurdex implant injection
  - BCVA change (ETDRS letters) from the last assessment prior to the first Ozurdex implant injection to 7-12 weeks following each Ozurdex implant injection
  - CRT by OCT change ( $\mu\text{m}$ ) from the last assessment prior to Ozurdex injection to 7-12 weeks following each Ozurdex implant injection
  - CRT by OCT change ( $\mu\text{m}$ ) from the last assessment prior to the first Ozurdex implant injection to 7-12 weeks following each Ozurdex implant injection

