### Relationship between reinjection interval and drug effectiveness

The potential relationship between Ozurdex reinjection interval and BCVA will be assessed by considering, for each Ozurdex injection  $j$  ( $j \geq 1$ ) in the study eye, the time interval between injection  $j$  and injection  $(j+1)$  and BCVA change from the value prior to injection  $(j+1)$  to 7-12 weeks following injection  $(j+1)$ . All injections of the patient will be considered all together for this analysis.

As a first approach, a figure (scatter plot) defined by Ozurdex reinjection interval (in months) on the horizontal axis and BCVA change (in ETDRS letters) on the vertical axis will be plotted. A linear regression line along with the spearman rank coefficient and p-value will be superimposed on the data of the scatter plot.

As a second approach, the median Ozurdex reinjection interval will be calculated considering all reinjection intervals for a patient. BCVA change (in ETDRS letters) will be then summarized using descriptive statistics by reinjection intervals categorized in two classes according to the median ( $\leq$  median;  $>$  median). The 95% CI of the mean BCVA change will be provided in each class. Based on the observed distribution, other categories than the median may be considered to categorize the reinjection interval.

The same analysis will be performed considering, for each Ozurdex injection  $j$  ( $j \geq 2$ ) in the study eye, the time interval between injection  $j$  and injection  $(j+1)$  and BCVA change from the value prior to the first Ozurdex injection in the study eye (=baseline value) to 7-12 weeks following injection  $(j+1)$ .

A similar analysis will be performed to assess the potential relationship between reinjection interval and CRT in the study eye.

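### SAP 15.2.1 starts the interval-versus-change-from-baseline analysis at j ≥ 2, which leaves out the first reinjection interval and every patient with exactly two implants

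*SAP*

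**What the plan says.** The part of SAP 15.2.1 on the relationship between interval and effectiveness sets out two BCVA analyses.

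- **Change from the value before the reinjection.** For every j ≥ 1, the interval from injection j to j+1 is paired with the BCVA change from just before injection j+1 to 7-12 weeks after it.
- **Change from baseline.** This is introduced as the same analysis but is restricted to "j \geq 2$ ) in the study eye, the time interval between injection" j and j+1. The paired outcome is the "BCVA change from the value prior to the first Ozurdex injection in the study eye (=baseline value) to 7-12 weeks following injection" j+1.

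For CRT the SAP gives no index. It says only: "A similar analysis will be performed to assess the potential relationship between reinjection interval and CRT in the study eye".

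Earlier in 15.2.1 the outcome list has no such restriction: "BCVA change (ETDRS letters) from the last assessment prior to the first Ozurdex implant injection to 7-12 weeks following each Ozurdex implant injection". SAP 15.1 defines intervals from j = 1.

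Protocol 14.2.2.3.1 takes as its units the "second injection or first reinjection, third injection or second reinjection" and so on. It extends the scatter plot to the longer-term outcome: "The same scatter plot will be done for the change in BCVA and CRT from time of first implant injection to 7-12 weeks following each" injection. It does the same for the categorised interval: "BCVA and CRT change from time of first implant injection to 7-12 weeks following each Ozurdex implant injection will be described by these categories". The Figure 1 legend assigns an outcome to Time interval 1: "BCVA and CRT change from measurement 1 to measurement 2 will be considered".

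**The concern.** Both versions follow up injection j+1, so they should admit the same intervals. Raising the start from j ≥ 1 to j ≥ 2 removes the pair formed by the first reinjection interval and the change from baseline after the second implant. Inclusion criterion 1 requires only two implants in the study eye, so a patient with exactly two has that pair and no other.

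Three consequences follow.

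1. The change-from-baseline analysis is confined to patients who went on to a third implant, a selection the protocol does not plan.
2. That selection is tied to the exposure. Patients with long intervals are less likely to reach a third implant within follow-up, so the range of intervals on the horizontal axis may be narrowed.
3. The two versions would rest on different patients and intervals. A difference between their Spearman coefficients could not be put down to the choice of outcome alone.

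**Working it through.** **The plan's own figure.** The documents give no count of intervals for this analysis. The only sample-size figure for the interval is the precision of its mean, ω = 1.96 × SD / √n with n = 150. SDs of 1.5, 2.0, 2.5 and 3.0 months give 0.240, 0.320, 0.400 and 0.480, which round to the stated 0.2, 0.3, 0.4 and 0.5. That figure reproduces and does not depend on this point.

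**Pairs admitted by each index.** A pair is (interval j to j+1, outcome after j+1).

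| Implants in study eye | Pairs with j ≥ 1 | Pairs with j ≥ 2 |
|---|---|---|
| 2 | 1 | 0 |
| 3 | 2 | 1 |
| 4 | 3 | 2 |
| 5 | 4 | 3 |
| 6 | 5 | 4 |

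Each patient loses exactly one pair, and a two-implant patient loses the only one.

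**Comparison with SAP 21.3.5.** That section also uses j ≥ 2 for change from baseline, but there j is the injection being followed up. Call the followed-up injection k.

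- In 21.3.5, k = j, so j ≥ 2 means k ≥ 2 and injection 2 is included.
- In 15.2.1, k = j + 1, so j ≥ 2 means k ≥ 3 and injection 2 is excluded.
- The 15.2.1 index that matches 21.3.5 is j ≥ 1.

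The restriction k ≥ 2 is reasonable because, after injection 1, change from baseline and change from the prior value are the same quantity. After injection 2 they differ, so the omitted pair is not redundant.

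**Size.** Take N = 150 (SAP Section 19) and let m be the mean number of reinjections per patient, at least 1 by inclusion criterion 1. The documents do not give m, so the values below are assumed.

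- Pairs with j ≥ 1: 150m
- Pairs with j ≥ 2: 150(m − 1)
- Share lost: 150 / 150m = 1/m

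| Assumed m | Pairs, j ≥ 1 | Pairs, j ≥ 2 | Share lost |
|---|---|---|---|
| 6 | 900 | 750 | 16.7% |
| 4 | 600 | 450 | 25.0% |
| 3 | 450 | 300 | 33.3% |
| 2 | 300 | 150 | 50.0% |
| 1.5 | 225 | 75 | 66.7% |

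**Patients lost entirely.** Let p be the share with exactly one reinjection. All others have at least two, so m ≥ p + 2(1 − p), which gives p ≥ 2 − m. At m = 1.5, p is at least 50%, or 75 of 150 patients. For m of 2 or more the bound is uninformative. If p were between 20% and 60% (assumed), 30 to 90 of 150 patients would drop out.

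**Ceilings.** These pair counts are maxima. A pair also needs an assessment in the 7-12 week window, and SAP 21.2 ends follow-up at the first concomitant anti-VEGF or corticosteroid treatment.

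**Link to interval length (illustration).** Guaranteed follow-up is 12 months. Using the lowest and highest mean intervals cited in SAP Section 19, a third implant would fall at 2 × 4.7 = 9.4 months or 2 × 6.7 = 13.4 months. The second lies beyond the guaranteed follow-up, even before adding the outcome window.

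**The case against.** The strongest reply is that this is an index slip. The j ≥ 2 of SAP 21.3.5 appears to have been carried into a paragraph where the followed-up injection is j+1. The surrounding text points to the full set of reinjections, the variables for injection 2 are already defined, and the table and figure specifications are in a separate document that may have the index right. On that view the missing Section 22 entry is only a consequence of the slip. This is plausible, but it is inference. The SAP as written is the rule, and that rule gives the wrong analysis set.

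Three narrower points are fair.

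- The Figure 1 legend describes change from the value before each reinjection, which the SAP indexes correctly. It shows that the protocol counts the first interval. The case on change from first injection rests on the scatter-plot and category sentences.
- The CRT index is unstated, so the omission there is the natural reading of the text, not its letter.
- The 1/m share assumes every patient supplies a first pair and that missing window values fall evenly across injections. Departures could move the share either way, and m itself is unknown.

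The reach is also limited. The study tests no hypothesis and claims no causal conclusions. Interval 1-2 remains in the primary analysis and in the j ≥ 1 relationship analysis, and change from baseline after injection 2 is still summarised descriptively. These points limit the importance of the error but do not remove it.

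**Conclusion.** The concern holds. As written, the change-from-baseline version of the relationship analysis omits the first reinjection interval for everyone and excludes patients with exactly two implants. This departs from Protocol 14.2.2.3.1 and from the SAP's own outcome list. No reason is given, and Section 22 lists only two changes, neither of them this one.

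The firm statement of size is up to one pair per patient: at most 150 for BCVA and, if the index carries over, at most 150 for CRT. As a share that is 17% to 67% for assumed m from 6 down to 1.5. The documents do not fix where in that range the study will fall, or how many patients have exactly two implants. The effect is confined to one version of a secondary, exploratory analysis, together with the subgroup runs that Table 6-1 plans for this objective. It should be corrected, but it does not threaten the primary objective.

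**What to change.** In the change-from-baseline paragraph of SAP 15.2.1, replace j ≥ 2 with j ≥ 1, and state the index explicitly for both CRT versions. A short note that j+1 is the followed-up injection here, whereas j is in 21.3.5, would prevent the same confusion in programming. Check that the separate table and figure specifications use the same index.

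If the restriction to the second reinjection onwards is intended, give the reason in 15.2.1 and list it in Section 22 as a change from the protocol.

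The cost is a revision of SAP V1.0 and one check of the specifications. No new data are needed.

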#### **15.2.2 Second Secondary Objective**

The secondary objective '*To describe the reasons for reinjection*' will be assessed considering the primary reason for injection (Disease progression, Lack of effect, Other) reported at each follow-up visit at which an Ozurdex injection was performed in the study eye. The analysis will be summarized using descriptive statistics.

For the study eye, the primary reason for injection (Disease progression, Lack of effect, Other) will be first summarized for each reinjection (i.e. first reinjection, second reinjection, etc.). Then, the primary reason for injection will be described considering all reinjections (the denominator for percentages will be the total number of reinjections in the study eye). Reasons reported as free texts in the 'Other' category will be summarized in a listing.

### 15.2.3 Third Secondary Objective

The secondary objective '*To assess drug effectiveness in patients who are naïve of any anti-VEGF treatment*' will be assessed by carrying out analyses detailed in the paragraph '*Description of drug effectiveness*' in Section 15.2.1 in the subgroup of patients who are naïve of any anti-VEGF treatment in the study eye prior to the first Ozurdex injection in the study eye vs. patients who received at least one anti-VEGF treatment in the study eye prior to the first Ozurdex injection in the study eye. Comparison between both subgroups will be purely descriptive (no statistical tests will be computed).

In addition, a subgroup of patients will be identified by the number of anti-VEGF treatments in the study eye prior to the first Ozurdex injection in the study eye. The number of treatments will be categorized: 0, 1 to 3, 4 to 6,  $>6$  [DV].

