The chance of spontaneous improvement in the best-corrected visual acuity (BCVA) and decrease in CRT is limited, so the prognosis of DME without appropriate treatment is generally disappointing. Several therapeutic options are available. Focal and grid laser photocoagulation has represented the standard of care for treatment of DME prior to the introduction of intravitreal approach, i.e. anti-vascular endothelial growth factor (anti-VEGF) and corticosteroids. Approved anti-VEGF therapies include ranibizumab (Lucentis®, Novartis) and afibbercept (Eylea®, Bayer HealthCare). Even though not currently approved, bevacizumab (Avastin®, Genetech/Roche) is also used off-label for the treatment of retinal diseases, including DME. Anti-VEGF agents restore vision in a substantial proportion of treated patients. However, drawbacks have been identified for anti-VEGF patients: patients treated with anti-VEGF may be at increased risk to develop systemic (thromboembolic) adverse events (AEs) compared with sham/laser treatment arms; treatment

with anti-VEGF require monthly injections at the clinic for an extended period of time; and some patients are partial or non-responders to anti-VEGF treatments. Corticosteroids therapy, through anti-inflammatory properties, and VEGF inhibition, inhibit many of the inflammatory processes known to be involved in the progression of DME. Commercially available corticosteroids compounds for intravitreal use include fluocinolone (Iluvien®, Alimera Sciences) and Ozurdex®. Even though not approved for this indication, triamcinolone acetonide is also used off-label for the treatment of DME. Long-acting corticosteroid implants such as Iluvien and Ozurdex have the benefit of reducing the number and frequency of injections. In the European Society of Retina Specialists (EURETINA) guidelines for the management of DME, the importance of corticosteroids in the armamentarium of drugs for treating DME patients is recognized; however corticosteroids are recommended to be administered in non-responders who have already been treated with anti-VEGF. First line therapy with Ozurdex should be considered in patients with history of major cardiovascular events and in patients that are not willing to come for monthly injections in the first 6 months of therapy.

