#### Description of drug effectiveness in the study eye

As preliminary description of drug effectiveness, BCVA in the study eye will be described at baseline and during the follow-up period using descriptive statistics for the following parameters:

- Last BCVA (ETDRS letters) prior to each Ozurdex injection [DV]
- BCVA (ETDRS letters) at 7-12 weeks following each Ozurdex injection,
- Change in BCVA (ETDRS letters) from baseline to 7-12 weeks following each Ozurdex injection [DV],
- Change in BCVA (ETDRS letters) from the value prior to Ozurdex reinjection to 7-12 weeks following each Ozurdex reinjection [DV].

Note: See the rule defined in Section 21.2 in case several measurements are available within the 7-12 week time window.

A similar description will be performed for CRT ( $\mu\text{m}$ ) in the study eye, regardless of the technology used for CRT measurement (confocal scanning laser ophthalmoscope; OCT; OCT – angiography; retinal thickness analyser; ultrasound).

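### Baseline BCVA and CRT are reported for anti-VEGF-naive and pretreated eyes but not used when their changes are compared

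*SAP*

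**What the plan says.** The third secondary objective (Protocol 6.1.2, SAP 5.0) is effectiveness in patients naive to anti-VEGF. Protocol 14.2.2.3.3 summarises change in that subgroup only. SAP 15.2.3 adds a contrast with patients who had at least one earlier anti-VEGF treatment in the study eye, and also defines groups with 0, 1 to 3, 4 to 6 and more than 6 earlier treatments. On the two-group contrast it says: "Comparison between both subgroups will be purely descriptive (no statistical tests will be computed".

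The quantities compared are those of the effectiveness description in SAP 15.2.1. There, "BCVA in the study eye will be described at baseline and during the follow-up period using descriptive statistics". The list covers the last value before each injection, the value at 7-12 weeks, the change from the pre-reinjection value, and "Change in BCVA (ETDRS letters) from baseline to 7-12 weeks following each Ozurdex injection". For thickness, "A similar description will be performed for CRT". Starting BCVA and CRT are therefore tabulated for each group. Neither section specifies a comparison of change that is adjusted for, or stratified by, the starting value.

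The confounding text (Protocol 7.3.3, SAP 7.0) proposes a remedy for safety events only. Effectiveness is not covered.

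**The concern.** An eye with poor acuity has more room to gain letters, and a thick retina has more room to thin. Where change depends on the starting value in this way, two groups with different starting values will show different mean changes even if the implant works equally well in both.

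There is reason not to take balance for granted. Whether an eye was treated with anti-VEGF first was a clinical decision. Selection also differs: Protocol 9.2 describes consecutive selection within country quotas, and a separate competitive search for naive patients.

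What is at stake is the reading of two mean changes placed side by side. Omitting a test does not remove the effect of an imbalance. Seeing the baseline means tells a reader that an imbalance exists, but not how many letters of the difference it explains.

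**Working it through.** **Inputs from the documents.** Total 150 patients, up to 50 of them naive (SAP 4.0, 19.0). SD of BCVA change 4.5 to 10.0 letters (SAP Table 18-2). Intervals two-sided at 95% (SAP 21.1). Planned contrast: 50 against 150 − 50 = 100.

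**The plan's own figure.** Half-width = 1.96 × SD / √n with n = 50:

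- SD 10.0: 1.96 × 10.0 / √50 = 2.77 (stated 2.8)
- SD 8.0: 2.22 (stated 2.2)
- SD 6.0: 1.66 (stated 1.7)
- SD 4.5: 1.25, which rounds to 1.2 (stated 1.3; a rounding slip with no bearing here)

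These describe one mean. The contrast needs the half-width of a difference.

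**Half-width of the difference, 50 against 100.** 1.96 × SD × √(1/50 + 1/100) = 1.96 × SD × 0.1732:

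- SD 4.5: 1.53
- SD 6.0: 2.04
- SD 8.0: 2.72
- SD 10.0: 3.39

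Eyes without a value in the 7-12 week window would drop out, so the real intervals would be wider.

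**Shift from a baseline imbalance.** With no true difference between groups, shift = slope × baseline gap. The documents give neither quantity, so both are assumed. The slope is the number of letters of gain lost per letter of better baseline.

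| Slope | Gap 5 letters | Gap 10 letters |
|---|---|---|
| 0.1 | 0.5 | 1.0 |
| 0.2 | 1.0 | 2.0 |
| 0.3 | 1.5 | 3.0 |
| 0.5 | 2.5 | 5.0 |

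Four of the eight entries exceed 1.53 (SD 4.5), and a fifth, 1.5, is almost equal to it. Only one exceeds 3.39 (SD 10). The steep slopes do not sit easily with the small SD: a slope of 0.5 with a change SD of 4.5 requires a baseline SD of at most 4.5 / 0.5 = 9 letters.

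**Check by simulation.** Assumptions: 50 naive and 100 pretreated, no true group effect, baseline SD 12, change SD about 10, naive eyes starting lower, 1,000 runs per setting.

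| Slope | Gap | Mean raw difference | Mean adjusted difference |
|---|---|---|---|
| 0.2 | 5 | 1.05 | 0.06 |
| 0.2 | 10 | 1.92 | −0.09 |
| 0.3 | 5 | 1.57 | 0.07 |
| 0.3 | 10 | 2.93 | −0.07 |
| 0.5 | 5 | 2.45 | −0.03 |
| 0.5 | 10 | 5.03 | 0.03 |

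The raw differences match slope × gap, and adjustment for baseline brings them within 0.1 of zero. The simulation builds in a linear dependence on baseline. It shows that the model removes that part, not that the dependence has this size in these patients.

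**The case against.** A reader might infer that the groups are compared with no sight of where they started. The documents do not support this. SAP 15.2.1 reports BCVA and CRT before each injection, SAP 15.2.3 applies that description to both groups, and lens status is described at baseline (SAP 12.1) and defines a subgroup (SAP 6.3).

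A reader might also infer that the plan would present an imbalance as a drug effect. It does not. The comparison is untested, the objectives rest on no hypothesis (Protocol 6), and causal conclusions are disclaimed (Protocol 8.2, SAP 4.0). Misreading is possible but not built in.

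Nor can one infer that the pretreated eyes are mainly anti-VEGF failures. Protocol 5.1 says that "corticosteroids are recommended to be administered in non-responders who have already been treated with anti-VEGF", but it is reporting a guideline. It does not describe the enrolled patients or their starting acuity or thickness.

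The objective itself concerns naive patients, and the precision in SAP Table 18-2 was planned for their mean alone. An imbalance against pretreated eyes leaves that mean untouched.

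Finally, raw and adjusted change answer different questions in non-randomised groups, and neither is correct by default. Measurement error in baseline contributes to the slope, and adjusting for that part can over-correct when true baselines differ. For reinjections, the pre-reinjection value is measured after the first implant, so adjusting for it could remove part of the effect being described.

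All of this stands. It limits the point to a supplementary analysis and dictates how the model should be set up. It does not answer the remaining gap: the SAP makes a contrast and gives no means of judging how much of it baseline explains.

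**Conclusion.** The point holds as a cheap improvement. Baseline BCVA and CRT are shown by group but not used in the comparison of change, so a baseline imbalance could be misread as a difference in effectiveness. Its direction and size cannot be known from the documents. Over the assumed slopes (0.1 to 0.5) and baseline gaps (5 to 10 letters), the shift is 0.5 to 5.0 letters, against a half-width for the difference of about 1.5 to 3.4 letters. It therefore ranges from minor to larger than sampling error. No size is given for CRT, because the documents state no SD for CRT change. The stronger reading, that the third secondary objective fails or its result is biased, is not supported.

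**What to change.** In SAP 15.2.3, keep the raw means and add beside them the adjusted mean change in each group and the adjusted difference with a 95% CI, without a p-value. Use a linear model with three terms: group (naive or pretreated), the BCVA (or CRT) value before the first Ozurdex injection, and baseline lens status.

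Fit it to the change from the first-injection baseline to 7-12 weeks after the first injection and, separately, to 7-12 weeks after the first reinjection. Do not adjust for the pre-reinjection value, which is post-treatment. Put the baseline values in the same table as the changes.

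Add a sentence saying that raw and adjusted change answer different questions here, that other differences between the groups (for example DME duration, retinopathy severity and earlier steroid treatment) remain unadjusted, and that the result stays descriptive.

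The cost is one small model per outcome and time point, that is 2 × 2 = 4 models, on data already collected. The planned sample size and precision figures do not change.
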